8.5. Subject Withdrawal Criteria

An early termination occurs when a subject who provides written informed consent ceases participation in the study, regardless of circumstances, before the completion of the study. Subjects may be voluntarily discontinued from study medication or withdrawn from the study at any time for any reason. In addition, the Principal Investigator or Medical Monitor may discontinue the study drug administration or terminate a subject's study participation due to any of the following reasons:

- AE (e.g., not compatible with study continuation)
- Non-compliance with study drug
- Lack of efficacy (e.g., IOP exceeds 34 mmHg in either eye after randomization)
- Progressive disease

- Protocol deviation (e.g., not fulfilling eligibility criteria)
- Pregnancy
- Voluntary withdrawal by subject at any time for any reason
- Lost to follow-up (e.g., no contact is possible)
- Death
- Other

If the study drug administration is discontinued prior to Visit 5, they should be encouraged to still participate in follow-up study visits until Visit 5 on an observational basis.

[figure not shown]
If the study drug administration is discontinued prior to Visit 5, then to the extent possible, all procedures for Early Termination will be performed on the day of early drug discontinuation as per [Table 3](#) (for adult subjects) or [Table 4](#) (for pediatric subjects). Subjects who are discontinued from the study early will not be replaced.

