### **3.4. Visits and Assessments**

There are 5 scheduled visits for pediatric subjects and 9 scheduled visits for adult subjects. Assessments at each visit and the time/visit window for each post-baseline assessment are specified in the Assessment Schedule for adult ([Table 1](#)) and pediatric subjects ([Table 2](#)), respectively.

If the study drug administration is discontinued prior to Visit 5 (end of the double-masked treatment period), the subject should be encouraged to still participate in follow-up study visits until Visit 5 on an observational basis. For subjects whose study participation is terminated prior to Visit 8 (Month 12), to the extent possible, all assessments scheduled for Visit 8 (Month 12) will be performed at the Exit Visit.

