**Table 3: Definitions for Treatment Start and End Dates by Treatment Period**

| Treatment Period                    | Treatment Start Date   | Treatment End Date   |
|-------------------------------------|--|--|
| Double-Masked (DM) Treatment Period | The date at which a randomized subject takes the first dose of the DM study drug       | 
The date at which a randomized subject takes the last dose of the DM study drug. If the date of the last dose is missing and the subject does not receive any OL study drug:
 
 
• The day before the Visit 5 (Month 3) date will be considered the treatment end date for subjects who completed the Month 3 Visit
 
• The day before the Exit Visit date will be used for subjects who prematurely discontinued from the study before Visit 5 (Month 3). If the Exit Visit date of a non-completer is not available, then the day before the last available visit date will be considered the treatment end date
 
 |
| Open-Label (OL) Treatment Period    | The date at which a randomized adult subject takes the first dose of the OL study drug | 
The date at which a randomized adult subject takes the last dose of the OL study drug. If the date of the last dose is missing:
 
 
• The day before the Visit 8 (Month 12) date will be considered the treatment end date for subjects who completed the Month 12 Visit
 
• The day before the Exit Visit date will be used for subjects who prematurely discontinued from the study during OL period. If the Exit Visit date of a non-completer is not available, then the day before the last available visit date will be considered the treatment end date
 
  |

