## 4.4. Safety-Related Definitions

### 4.4.1. Adverse Event

Under Protocol 011709IN, an AE is defined as any untoward medical occurrence that occurs in a study subject, regardless of the causal relationship with the study treatment. An *on-study* AE can occur any time after the date of informed consent through the last study visit. An AE will be considered as *treatment-emergent* if the onset date of the AE occurred on or after the treatment start date till up to 2 days (twice the scheduled dosing interval) after treatment end date.

Treatment-emergent AEs (TEAEs) are a subset of on-study AEs. Both on-study and TEAEs will be collected, but only TEAEs will be tabulated.

The severity of each AE will be graded by the Clinical Investigator as Mild, Moderate, or Severe. AEs will also be rated by the Investigator as to their causality/relationship to the study drug.

Each AE will be classified into a system organ class (SOC) and coded to a preferred term (PT) using Medical Dictionary for Regulatory Activities (MedDRA), Version 21.1 published in 2018.

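### For subjects who stop masked drug early and never start open-label DE-117, AEs beginning more than 2 days after the last dose are listed but not tabulated by treatment

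*SAP*

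**What the plan says.** SAP 4.4.1 separates two classes of event. The wider one is everything collected: "An *on-study* AE can occur any time after the date of informed consent through the last study visit". The narrower one is the treatment-emergent AE (TEAE), whose onset must fall "on or after the treatment start date till up to 2 days (twice the scheduled dosing interval) after treatment end date". Only the narrower class goes into tables: "Both on-study and TEAEs will be collected, but only TEAEs will be tabulated".

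The window is tied to the treatment end date. SAP Table 3 defines this for the double-masked period as "The date at which a randomized subject takes the last dose of the DM study drug", and for the entire study as the last dose of any study drug.

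Subjects who stop drug before Visit 5 are not meant to leave. SAP 3.4 says "the subject should be encouraged to still participate in follow-up study visits until Visit 5 on an observational basis", and Protocol 8.5 says the same. Protocol 12.1.1.2 requires AEs to be recorded until withdrawal or the scheduled exit visit. On the timing of the termination exam, Protocol 8.5 says that "to the extent possible, all procedures for Early Termination will be performed on the day of early drug discontinuation". SAP 3.4 places the exit assessments of subjects who leave early at the Exit Visit.

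SAP 9.1 lists non-TEAEs separately. Protocol 14.8 plans to tabulate subjects with any AE and gives no onset limit. SAP Section 10, which records departures from the protocol's analyses, covers the FAS definition, a key secondary endpoint and the removal of LOCF. It does not mention the TEAE restriction.

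**The concern.** The plan collects safety data after early stopping and then leaves most of it out of the tables that compare the arms. The subjects affected include those who stopped because they did not tolerate the drug. They stay in the Safety Population denominator, while their later events cannot enter the numerator of the AE, SAE, SAR or ESI tables. This applies even to an event that the investigator rates as related.

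The safety objective is a comparison with timolol, and Protocol 12.1.3 says macular edema has been reported in earlier DE-117 trials. Scheduled ophthalmoscopy after baseline takes place only at Visit 5 and at Visit 8 or early termination (Protocol 21.3.12). For an early stopper, the first scheduled fundus exam on study may therefore come after the last dose.

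There is also a consistency problem. SAP 9.1.1 to 9.1.3 build the ocular inflammation, macular edema and cosmetic-change summaries from AEs that developed in the course of the study, with no TEAE limit. Two programmers could produce different tables from the same SAP.

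**Working it through.** **1. The plan's own figure.** SAP 4.4.1 describes its 2-day tail as twice the dosing interval. A once-daily interval gives 2 × 1 day = 2 days, which reproduces it. The masked regimen is instilled twice daily in both arms (Protocol 9.3), and that would give 2 × 0.5 = 1 day. The stated basis thus fits once-daily dosing only. This is a side remark and does not show that 2 days is too short.

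**2. Whether the entire-study tables recover the events.** They do not. For a subject who never takes open-label drug, the last dose of any study drug is the last masked dose, so both end dates in Table 3 coincide.

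**3. Untabulated days for one subject.** Visit 5 is Day 91 ± 7. Untabulated days = Visit 5 day − (last-dose day + 2). The last-dose days are illustrative.

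| Last dose | Window closes | Visit 5 on Day 84 | Day 91 | Day 98 | Share of post-drug follow-up, Day 91 |
|---|---|---|---|---|---|
| Day 8 | Day 10 | 74 | 81 | 88 | 81/83 = 98% |
| Day 43 | Day 45 | 39 | 46 | 53 | 46/48 = 96% |
| Day 75 | Day 77 | 7 | 14 | 21 | 14/16 = 88% |

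**4. Size over the trial.** Assume that 5% to 10% of the 400 adults stop early (20 to 40 subjects), that last doses are spread evenly over Days 2 to 90, and that all these subjects stay to Day 91 without starting open-label drug.

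- Mean untabulated days: the sum of max(0, 89 − d) over d = 2 to 90 is 87 × 88 / 2 = 3,828; 3,828 / 89 = 43.0.
- Total: 20 × 43.0 = 860 and 40 × 43.0 = 1,720 subject-days.
- Denominator: 400 × 91 = 36,400 subject-days.
- Share: 860 / 36,400 = 2.4%; 1,720 / 36,400 = 4.7%.

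**5. Date rules that change the result for some events.** If the last-dose date is missing for a subject who left before Visit 5, Table 3 uses the day before the Exit Visit. The window then runs to −1 + 2 = 1 day after that visit and covers the exit exam. An AE with no onset date at all counts as treatment-emergent (SAP Table 7), and partial onset dates are set to the first of the month or year. None of these rules brings back an event with known dates.

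**The case against.** An on-treatment window is a legitimate choice, and the SAP states a basis for it. Subjects off study drug may be using other IOP-lowering therapy, as Protocol 14.7 and SAP 6.2.1 anticipate. Counting their later events under the randomized drug would create an attribution problem of its own. Termination procedures are meant for the day of stopping, so a gap before that exam is the exception, and follow-up to Visit 5 is only encouraged. The AE that led to stopping will usually fall inside the window and be tabulated. Non-TEAEs, SAEs and ESIs are all listed, AE tables count subjects and not person-time, and no safety testing is planned. All of this stands. It argues for leaving the TEAE tables alone and keeping later events separate, not for having no tabulation of them.

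Three stronger readings are tempting, and the documents do not support them.

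- **A reader might infer that late macular edema is certain to be missing from the macular edema summary.** The wording of SAP 9.1.2 could include it, and 4.4.1 would exclude it; the SAP does not say which governs. An abnormal macula could also reach a by-treatment table as an exam finding. Table 4 maps ophthalmoscopy from Day 2 onward to Month 3, and SAP 9.4 summarizes the shift at Month 3, unless an exam nearer Day 91 replaces the earlier one. BCVA and slit-lamp findings are likewise summarized by analysis visit.
- **A reader might set the 28-day beta-blocker washout against the 2-day tail.** That washout clears prior IOP-lowering drugs before baseline. The protocol does not present it as a period of adverse-effect carry-over, and it gives no such figure for DE-117.
- **A reader might infer that the safety comparison is biased toward one arm.** That needs early stopping, or events after stopping, to differ between arms. The documents give no rates.

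**Conclusion.** The point holds as a gap in tabulation, not in collection or listing. For subjects who stop masked drug early and never start open-label DE-117, a dated AE that begins more than 2 days after the last dose enters no by-treatment AE, SAE, SAR or ESI table. The SAP narrows what Protocol 14.8 describes without recording it, and 4.4.1 conflicts with 9.1.1 to 9.1.3.

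The 2.4% to 4.7% is a ceiling with respect to retention, for the assumed stopping rate and even spread of stopping times. Neither the rate nor full retention comes from the documents, and stopping concentrated early would leave more days uncovered per subject. The figure measures follow-up time; it does not estimate missed events or bias. No efficacy conclusion is touched. This is an inexpensive improvement to the safety report, not a flaw that threatens the trial's conclusions.

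**What to change.** 1. Leave the TEAE tables as they are.
2. For subjects who stop double-masked drug and do not start open-label DE-117, add a supplementary tabulation by treatment of SAEs, ESIs and ocular AEs that begin after the TEAE window closes, through the last visit of the double-masked period. Show it in its own after-last-dose column.
3. State in SAP 9.1.1 to 9.1.3 that those summaries include on-study events after the last dose, so that they no longer conflict with 4.4.1.
4. Record the restriction to TEAEs in SAP Section 10 as a change from Protocol 14.8.

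The cost is some SAP wording and one supplementary table from data already collected. The downside is that some of these events will be unrelated to study drug or will reflect other IOP-lowering therapy begun after stopping. Keeping the column separate shows them without mixing them into the on-treatment comparison.

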#### 4.4.1.1. Serious Adverse Event

An AE will be counted as a *serious adverse event* (SAE) if the Clinical Investigator selected “Yes” to the question ‘Is the adverse event serious?’ on the AE eCRF. Any AE is considered a SAE if it fulfills one or more of the following criteria:

- Death (i.e., the AE caused or led to death)
- Life threatening (i.e., immediately life-threatening)
- It required or prolonged inpatient hospitalization.
- It resulted in a persistent or significant disability/incapacity (i.e., the AE resulted in a substantial disruption of the subject’s ability to carry out normal life functions).
- It resulted in a congenital anomaly/birth defect in the offspring of a study subject who was exposed to study therapy prior to conception or during pregnancy.
- It is a medically significant event(s), which may include “sight-threatening events,” that may not meet any of the above serious criteria but may jeopardize the subject or require medical or surgical intervention to prevent one of the outcomes listed above.

#### 4.4.1.2. Ocular Adverse Event

An AE will be counted as an *ocular AE* if the Clinical Investigator selected “OD”, “OS”, or “OU” under ‘Eye(s) affected’ on the AE eCRF.

#### 4.4.1.3. Suspected Adverse Reaction

An AE will be counted as a *suspected adverse reaction* (SAR) if the Clinical Investigator answered ‘Related’ to the AE eCRF question “Relationship to Study Drug”.

#### 4.4.1.4. Events of Special Interest

*Events of special interest* (ESI) are pregnancy, clinically significant study medication administration error, and macular edema/cystoid macular edema.

#### 4.4.2. Other Safety Measures

[Table 6](#) lists the safety measures to be evaluated for this study.

**Table 6: Safety Assessments**

| Safety Measures | Note  |
|-----------------|---|
| BCVA            | Best-corrected visual acuity will be measured for each eye at each visit under normal room illumination using visual acuity chart (e.g., ETDRS chart) and the logMAR scoring will be recorded in the subject’s source document. Increase in logMAR scores means worsening in visual acuity. |

**Table 6: Safety Assessments (Continued)**

| Safety Measures                       | Note  |
|---------------------------------------|---|
| Slit-lamp Biomicroscopy               | Slit-lamp biomicroscopy examinations (severity scores for 12 parameters: lid hyperemia, lid edema, conjunctival hyperemia, conjunctival chemosis, corneal staining, corneal edema, keratic precipitate, anterior chamber cells, anterior chamber flare, anterior synechiae of iris, posterior synechiae of iris, and cataract) will be performed and graded immediately before the 8:00 IOP measurement at all visits except Visit 1/1a (Screening or mid-washout visit). Cataract severity will be assessed for phakic eyes.           |
| Ophthalmoscopy                        | The ophthalmoscopy (fundus) examination will be performed for each eye at Visit 1, Visit 2, Visit 5, and Visit 8/ Study Exit/Early Termination. Variables from ophthalmoscopy are cup-to-disc ratio, glaucomatous optic nerve severity, and assessments of vitreous, retina, macula, and choroid.   |
| Eyelid Sulcus, eyelid, and iris color | The investigator (or his/her designee) will take front- and side-view photographs of each eye at Visit 2 (Baseline). The photographs must include the iris, eye lids and eyelashes of each eye. The photographs taken at Visit 2 (Baseline) will be used to help the Investigator assess any changes (“No changes”, “Increased”, or “Decreased”) from baseline in eyelid, eyelashes, and iris color at each follow-up visit, and assess for DUES (“Yes”, “No”) at Visit 5, Visit 6, Visit 7, and Visit 8/ Study Exit/Early Termination. |
| Vital Signs                           | Resting blood pressure and pulse rate will be collected at Visit 1, Visit 2, Visit 5, and Visit 8/ Study Exit/Early Termination.  |

## 4.5. Other Definitions

### 4.5.1. Prior and Concomitant Medications

Non-study medications will be categorized into prior medications and concomitant medications. Specifically, *prior medication* is defined as any non-study medication taken and ended prior to the study medication start date. *Concomitant medication* is defined as any non-study medication taken concurrently while receiving study medication, i.e., the treatment period (period of time from first dose to last dose) of a concomitant medication taken by a subject must overlap with the treatment period (period of time from first dose to last dose) of the study medication.

All prior and concomitant medications will be coded using the World Health Organization (WHO) Drug Global, Version September 2018, format B3. Each prior or concomitant medication will be classified using the Anatomical-Therapeutic-Chemical (ATC) classification system and mapped to a WHO Drug preferred drug name.

**4.5.2. Concurrent Medical Conditions**

Concurrent medical conditions are those ongoing conditions or diseases that are present at the signing of informed consent.

### **5.1. Intent-to-Treat Population**

The *intent-to-treat* (ITT) population will include all randomized subjects.

### **5.2. Safety Population**

The Safety Population will include all randomized subjects who received at least one dose of the study medication. Safety analyses will be performed using the Safety Population and summarizing by actual treatment received.

### **5.3. Full Analysis Set**

The Full Analysis Set (FAS) will include all randomized subjects who received at least one dose of study medication and provided Baseline IOP data (at any timepoint) and at least one post-baseline IOP measurement (at any timepoint). Efficacy analyses will be performed using the FAS and summarized by treatment as randomized.

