14.4.2. Full Analysis Set

The Full Analysis Set (FAS) will include all randomized subjects who received at least one dose of study medication and provided at least one post-baseline IOP measurement. The efficacy analysis will be performed on the FAS or a subset of the FAS by planned treatment.

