## 6.2. Handling of Missing Data

### 6.2.1. Efficacy Measures

For subjects with the use of any non-study IOP-lowering therapy to lower IOP, unless otherwise specified, the IOP data collected after the non-study IOP-lowering therapy will be censored (treated as missing) in efficacy analyses in both double-masked and open-label periods.

For efficacy measures during double-masked period,

- For each IOP endpoint, no imputation is needed for the analysis on observed cases using the mixed-effects model for repeated measures (MMRM). Sensitivity analysis will be performed using a Pattern-Mixture Model (PMM) approach.
- In the PMM approach, Multiple Imputation (MI) with mixed missing data mechanisms will be used to investigate the appropriateness of the missing at random (MAR) assumption for missing values resulting from censoring due to the use of IOP-lowering rescue therapy, or resulting from study discontinuation due to lack of efficacy or AE.

For efficacy measures during open-label treatment period, no inferential analysis will be performed. Summary statistics will be provided for IOP and mean diurnal IOP for each scheduled visit, using observed data.

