## 7. SUMMARY OF STUDY POPULATION DATA

### 7.1. Subject Disposition

The disposition of ITT population (i.e., all randomized subjects) will be summarized by treatment period (double-masked and open-label) and by planned treatment (for double-masked period) and overall.

For the double-masked period, the summary will include the number and percentage of ITT subjects in the Safety population, FAS, and PPS. The disposition summary will also include the number and percentage of subjects who completed the study drug, subjects who discontinued the study drug prematurely but continued with study participation until the Month 3 Visit and among which who completed or not completed the Month 3 Visit, as well as the number and percentage of subjects who discontinued from the study or discontinued from the study drug prior to Month 3 Visit by the primary discontinuation reason.

For the open-label period, the summary will include the number and percentage of subjects who received any study treatment during open-label period, and subjects who are still on the study at the time of data cut (for reports other than the final clinical study report). The disposition summary will also include the number and percentage of subjects who completed the study drug, and subjects who discontinued from the study prior to Month 12 Visit by the primary discontinuation reason.

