**Table 8: Overview of Primary and Sensitivity Analysis Methods**

| Primary or Sensitivity Analysis | Statistical Method        | Analysis Population | Handling of Missing Data |
|---------------------------------|---------------------------|---------------------|--------------------------|
| Primary Analysis                | MMRM                      | FAS                 | Observed cases           |
| Sensitivity Analyses            | MMRM                      | PPS                 | Observed cases           |
|                                 | PMM with delta-adjustment | FAS                 | MI                       |

Abbreviations: FAS = full analysis set; MI = multiple imputation; MMRM = mixed-effects model for repeated measures; PMM = pattern-mixture model; PPS = per protocol set.

To assess the sensitivity to departure from MAR assumption, a PMM with delta-adjustment will be applied, as follows:

- a. Use Markov chain Monte Carlo (MCMC) to create monotone missingness first. Then obtain standard multiple imputations under MAR assumptions for missing IOP values using monotone regression. The missing data are filled in and 50 complete datasets are created. The seed that will be used in the SAS program is 13546.
- b. For each IOP value that had been missing because of (1) censoring after having received IOP-lowering rescue therapy; or because of (2) early study discontinuation due to lack of efficacy or AE, regardless of treatment arm, adjust these values by adding delta to the imputed values, where delta = 1.0 mmHg. The seed that will be used in the SAS program is 13546.
- c. Each of the 50 complete datasets will then be analyzed separately using the same MMRM as used for the primary analysis.
- d. The estimates obtained from the MMRM analysis of each complete dataset are combined for inference purposes.
- e. Repeat step b, c, d, with delta = 2.0, 3.0, 4.0, and 5.0 mmHg. The larger the value of delta that is required to reverse the conclusion of the primary analysis, the more robust the conclusion is considered to be.

The main part of the SAS code for the specified MMRM analysis and PMM are provided in [Appendix A](#) and [Appendix B](#), respectively.

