For the primary endpoint, in addition to the two types of sensitivity analyses described above, if the overall rate of study drug discontinuation due to lack of efficacy or AE is greater than 10% and the difference between the rate in the DE-117 and Timolol arms is greater than 5 percentage points, a trimmed mean analysis ([Permutt et al., 2017](#)) will be conducted as a sensitivity analysis.

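### The delta-adjusted sensitivity analysis omits subjects who stop for an adverse event before giving any post-baseline IOP; the group is probably small and the gap is cheap to close

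*SAP*

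**What the plan says.** **Who is in the FAS.** SAP 5.3 takes randomized subjects with at least one dose "and provided Baseline IOP data (at any timepoint) and at least one post-baseline IOP measurement (at any timepoint"). Protocol 14.4.2 sets the same condition after baseline: the subject must have "provided at least one post-baseline IOP measurement".

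**Where the stress test is run.** The relevant row of SAP Table 8 reads "PMM with delta-adjustment | FAS". Step b gives delta to values missing after rescue therapy or because of "early study discontinuation due to lack of efficacy or AE, regardless of treatment arm, adjust these values by adding delta to the imputed values". Delta starts at 1.0 mmHg, and step e says "Repeat step b, c, d, with delta = 2.0, 3.0, 4.0, and 5.0 mmHg". The larger the delta needed to overturn the conclusion, the more robust the SAP considers it.

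**What else is planned.** The other standing sensitivity analysis is an observed-case MMRM on the PPS, which is a subset of the FAS. A trimmed-mean analysis is run only "if the overall rate of study drug discontinuation due to lack of efficacy or AE is greater than 10" percent and the arms also differ by more than 5 percentage points. SAP 10.3 drops LOCF on the ground that the PMM is enough. An ITT population is defined in SAP 5.1, and its stated use is in SAP 7.1: "The disposition of ITT population (i.e., all randomized subjects) will be summarized by treatment period". No efficacy analysis is assigned to it.

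**The concern.** SAP 6.2.1 says that the PMM is there to question missing-at-random for values censored after rescue "or resulting from study discontinuation due to lack of efficacy or AE". A subject who takes a few doses, stops for an adverse event before Week 1 and gives no exit reading is a clear example of that missingness. The FAS condition removes this subject before imputation starts.

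The method does not require this. An observed-case MMRM cannot use a subject with no outcome, but multiple imputation can, from treatment arm and baseline. Adult inclusion criterion 9 requires IOP at 08:00, 10:00 and 16:00 at Visit 2, so these predictors should exist for essentially every randomized adult.

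FAS membership also depends on what happens after randomization, and tolerability could influence it. The documents describe different profiles: the timolol package insert reports burning and stinging in about one in eight patients, and protocol 12.1.3 notes macular edema in DE-117 trials. They do not show which arm would lose more subjects early. At stake is how far a statement such as robust up to delta 5 can be taken, because it would cover only subjects with at least one post-baseline reading.

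**Working it through.** **1. Trace one subject.** Take a subject who was randomized and dosed, stopped for an adverse event, and has Visit 2 IOP but nothing later.

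| Analysis | Population | Subject included? |
|---|---|---|
| Primary MMRM | FAS | No |
| Sensitivity MMRM | PPS, within the FAS | No |
| Delta-adjusted PMM | FAS | No |
| Trimmed mean | Not stated, so FAS by the default in SAP 8; conditional | No |
| Disposition | ITT | Yes, as a count |

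An early loss of 1-3% would not by itself trigger the trimmed-mean analysis.

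**2. The plan's own power figure.** SAP 3.3 gives a margin of 1.5 mmHg, true difference 0, SD 4.0, correlation 0.6, 200 adults per arm, two-sided 5%, and 90% power.
- SE = 4.0 × √(2/200) = 0.40. Power at one timepoint is Φ(1.5/0.40 − 1.96) = Φ(1.79) = 96.3%.
- The full rule in SAP 8.1.1.1.1 needs all nine upper limits ≤ 1.5 and at least five ≤ 1.0. Simulating nine equally correlated differences (400,000 draws) gives 72%.
- The model adjusts for baseline IOP. With residual SD = 4.0 × √(1 − 0.36) = 3.2, the full rule gives 92.0% at correlation 0.6. It gives 94.2% at the residual correlation (0.6 − 0.36)/(1 − 0.36) = 0.375, and 90.5% with an assumed 10% dropout as well.

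So 90% is approached only under baseline-adjusted variants that the documents do not spell out. The present point does not depend on which was used.

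**3. Shift in the PMM difference.** Let kT and kC be the numbers in the DE-117 and Timolol arms who have no post-baseline IOP and qualify for delta. Imputation from arm and baseline should by itself move the expected difference little, so approximately:

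shift = delta × (kT − kC)/200

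The documents give neither kT nor kC. The range below is an assumption.

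| Net excess on DE-117 | delta 1 | delta 5 |
|---|---|---|
| 2 of 200 (1%) | 1 × 2/200 = 0.01 | 5 × 2/200 = 0.05 |
| 4 of 200 (2%) | 0.02 | 0.10 |
| 6 of 200 (3%) | 0.03 | 0.15 |

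Only the imbalance counts. Six against two gives 5 × 4/200 = 0.10 mmHg, equal counts give 0, and an excess on Timolol reverses the sign.

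**4. Scale against the nine-timepoint rule.** The same simulation with a common shift at all nine timepoints, true difference otherwise 0 and 200 per arm:

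| Shift (mmHg) | SD 4.0, corr. 0.6 | SD 3.2, corr. 0.6 | SD 3.2, corr. 0.375 |
|---|---|---|---|
| 0 | 72.4% | 92.0% | 94.2% |
| 0.05 | 67.0% | 88.8% | 91.1% |
| 0.10 | 61.3% | 84.7% | 87.0% |
| 0.15 | 55.3% | 79.7% | 81.5% |

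These are chances that the PMM meets the rule. They ignore the extra variance from imputation and any delta given to subjects already in the FAS.

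**The case against.** The strongest reply is that very few subjects fall through.
- Any single post-baseline reading keeps a subject in the FAS. Protocol 8.5 asks for early-termination procedures on the day the drug is stopped, to the extent possible, and those include IOP. Subjects are encouraged to keep attending to Visit 5, and the Week 1 analysis window opens on Day 2 (SAP Table 4).
- The protocol's example of lack of efficacy is an IOP above 34 mmHg after randomization, which presupposes a reading. A subject whose only readings follow rescue also meets the FAS wording. What remains is essentially adverse-event leavers with no reading at all.
- Early leavers for other reasons get no delta under step b. Adding them would only impute them under missing-at-random.

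All of this stands. It limits the size of the gap but does not close it, because exit procedures are done only where possible.

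A second reply is that a sensitivity analysis on the primary population changes one thing at a time, and that the FAS condition comes from the protocol. That is a fair rationale for the choice. It does not help a robustness claim about dropout when some dropouts were removed first.

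Third, the loss is partly visible already. SAP 7.1 counts FAS members by arm and discontinuations by reason, and SAP 9.1 tabulates adverse events leading to drug discontinuation. Only the cross-tabulation of FAS exclusions by reason is missing.

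A reader might infer that early dropouts in general escape the check, or that the trial's chance of success falls from 72% to 61%. Neither follows. Most early leavers should have an exit reading. The primary MMRM stays on the FAS, so that fall is the chance that the PMM meets the rule after a 0.10 mmHg shift, and its 72% starting point ignores the model's baseline adjustment.

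**Conclusion.** The point holds as a limited gap in the missing-data plan. The only unconditional missing-not-at-random analysis cannot see subjects who stop for an adverse event with no post-baseline IOP.

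Under an assumed net excess of 1-3% on DE-117, with every such subject qualifying for delta, the PMM difference would rise by 0.01-0.03 mmHg at delta 1 and by 0.05-0.15 mmHg at delta 5. It would not move if losses balance. A 0.10 mmHg shift lowers the chance that the PMM meets the full rule from about 92-94% to 85-87% at SD 3.2, or from 72% to 61% at raw SD 4.0. It matters mainly if upper limits lie close to 1.0 or 1.5 mmHg.

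The primary non-inferiority result would not change; the delta that reverses it might. The documents give no rate of such losses and no direction of imbalance, so they do not support a claim that the primary comparison is biased.

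**What to change.** In SAP 8.1.1.2 and Table 8, run the PMM on all randomized subjects who took at least one dose and have a Visit 2 IOP, whether or not they have a later reading. State this population explicitly: it is not the ITT population of SAP 5.1, and the dosing condition settles how never-dosed subjects are handled. Impute subjects with no post-baseline IOP from treatment arm and baseline IOP, and apply step b's delta when they discontinued for lack of efficacy or an adverse event. Keep the FAS for the primary MMRM. Record the change in SAP section 10, and report subjects excluded from the FAS by arm and reason beside the PMM result.

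The cost is small, since the data are already collected. The work is a revised table entry, a sentence on the imputation model (step a does not say that imputation uses arm and baseline), and a rerun on a slightly larger data set. The Appendix B code is not in the text available for review, so the programming effort cannot be confirmed. The tipping point may look slightly less favourable, and the PMM population will differ slightly from the primary one. If nobody is excluded from the FAS for want of a post-baseline reading, the PMM data set is unchanged.
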